- **Time Commitment**: Some participants may find the time commitment associated with this study too burdensome for their schedule. The study coordinator will discuss this time commitment prior to enrollment.
- Schedule Conflicts: Some participants may find it difficult to determine times they are available to come in for study visits. The study coordinator will also discuss preferred visit start times prior to enrollment to limit potential schedule conflicts.
- **Discomfort:** Participants may experience discomfort during blood and tissue sampling procedures and wish to discontinue the study. Prior to enrollment, the study coordinator will discuss all procedures and answer any questions participants may have concerning sampling procedures.
- **Unforeseen Reasons:** There may be other reasons participants may withdrawal from the research study that are unknown at this time.

Handling of Withdrawals

The participants right to withdraw from the study will be respected and will occur within the timeframe they request. In the event of a participant withdrawal, samples and data collected during their participation will be stored for future use or destroyed, based on the participants request.

Termination of Study

The research staff reserves the right to suspend/terminate subject's participation in this study at any time. This decision will be communicated to the participant and a reasonable effort will be made to mitigate/avoid this outcome. Potential study suspension/termination reasons include:

- **Ineligibility**: The subject's eligibility changes during the study
- Safety: The research has become harmful to the participant
- **Health**: The subject's health condition changes and requires treatment which affects the study outcomes
- **Incompliance**: Subject fails to follow the study guidelines
- Cancelation: The research study is canceled or suspended

Accountability Procedures for the Study Intervention

The research team will communicate internally weekly to discuss study progress and ensure all objectives and guidelines are met. From a participant perspective, agreement to enroll in the study will necessitate adherence to all study guidelines. The research staff will have regular contact (approximately 5 days/week) with subjects in the Aerobic Exercise group and will meet approximately twice monthly with the control group to monitor habits and study progress. We have found these interactions are indispensable for study adherence.

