The primary outcomes of this study involve collecting data at pre-aerobic exercise training and 12 weeks of training. Comparisons of trajectories across groups (training vs. Control) over time are made with appropriate adjustments for fixed (age, sex, medications, diabetes duration and severity) and time-varying covariates (i.e., weight, BMI, etc). Because of the anticipated nonlinear response curves of outcome variables we will use nonlinear mixed effects models to analyze our data. Using PROC NLMIXED in SAS 9.2 (SAS Inc.) we will fit the nonlinear models using two likelihood-based methods: adaptive Gaussian guadrature and a first-order Taylor series approximation [54-56]. The nonlinear mixed model is: $y = f(x_{ij}, \beta, u_i) + e_{ij}$, where f is some nonlinear function of known vector covariates (xij) for the jth observation on the jth subject, unknown fixed effect parameters (β), an unknown vector of random effect parameters (u_i), and unknown random errors (eii). For this study, we will treat training group as main fixed effect, intercept as random effects, and all outcomes will be used as responsive variables. Using nonlinear mixed effects models described above, we will reject null hypothesis if significant (p<.05) interaction effect between group and time is observed. Post-hoc analysis will examine differences between groups at different time points to assess the effect of exercise training on the outcome variables across time during the intervention. Our human sample size was determined using data from preliminary studies to provide adequate power after attrition to test the hypothesized effect of training on skeletal muscle RAGE and sRAGE concentrations. We will enroll 75 subjects with the anticipation that there will be 20-25% attrition at 12 weeks. We anticipate that the final N after attrition will be 60 (n= 30 per group). Using the two-sided alpha level of 0.05, we estimate that a total sample size of 60 will enable us to detect a pre-post, between-group difference of 1.24 standard units for RAGE between Aerobic Exercise training and Control groups with a target of 90% statistical power.

Safety and Efficacy Review

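### The p<.05 group-by-time test rests on maximum-likelihood standard errors with no small-sample correction, so at 60 completers it runs at about 5.4-5.8% (t) or 5.9-6.3% (z) instead of 5%

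*Combined protocol and SAP*

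**What the plan says.** All of the analysis text is in one paragraph, under Statistics and Sample Size Considerations.

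- **Estimation:** "Using PROC NLMIXED in SAS 9.2 (SAS Inc.) we will fit the nonlinear models using two likelihood-based methods". The two methods are adaptive Gaussian quadrature and a first-order Taylor approximation. Restricted maximum likelihood (REML) is not mentioned.
- **Model terms:** "we will treat training group as main fixed effect, intercept as random effects, and all outcomes will be used as responsive variables". The error part is described only as "an unknown vector of random effect parameters (u_i), and unknown random errors (eii"). No distribution, common variance or arm-specific variance is given.
- **Decision rule:** "we will reject null hypothesis if significant (p<.05) interaction effect between group and time is observed". The text does not say whether this is a Wald or a likelihood-ratio test, or on what degrees of freedom.
- **Size of the analysis:** "We anticipate that the final N after attrition will be 60 (n= 30 per group"), from 75 enrolled with 20-25% attrition. There is no split of attrition by arm.
- **Level:** "Using the two-sided alpha level of 0.05, we estimate that a total sample size of 60" is the basis of the power statement.

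The same paragraph places the primary data at two time points (before training and at 12 weeks) and names weight and BMI as time-varying covariates, with the list left open.

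**The concern.** Maximum likelihood estimates a variance by dividing the residual sum of squares by the number of observations. It makes no allowance for the fixed effects already estimated. In a large trial this does not matter. With 60 people and a handful of coefficients the standard error comes out slightly too small, and each p-value with it.

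The rule covers every outcome, so the same bias enters the test for primary sRAGE and for each secondary measure. When the arms are equally variable, it always acts towards rejecting too often. The confidence intervals are too narrow by the same factor.

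The unspecified residual variance is a second, conditional issue. Only one arm receives training, to which people may respond differently, so the spread of change may differ between arms. Whether that affects the error rate depends on how the variance is coded and on how many complete in each arm. The plan settles neither.

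**Working it through.** **Inputs from the plan:** N = 60 completers, 30 per arm; two time points; random intercept; two-sided 5% level; zero to two time-varying covariates (weight, BMI).

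**Assumptions, not in the plan:** a linear mean, since the nonlinear function is never given; a Wald test; and a t reference on subjects minus one random effect, 60 - 1 = 59, taken as the software default. Other references are shown below.

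**Step 1. Reduce the test.** With two visits, a random intercept and a linear mean, the interaction is the between-arm difference in mean change. Fixed covariates such as age and sex cancel from within-person differences. The coefficients that remain number k = 2, plus one for each time-varying covariate. Counting each such covariate in full is the upper end, because its coefficient also draws a little on between-person differences.

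**Step 2. The plan's own level.** With variance RSS/(N - k) and a t reference on N - k degrees of freedom, the size is 5.0% by construction. That is the figure the plan intends.

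**Step 3. Under maximum likelihood.** The variance is RSS/N, so the standard error is sqrt((N - k)/N) of the correct one:

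- k = 2: sqrt(58/60) = 0.983, or 1.7% too small
- k = 3: sqrt(57/60) = 0.975, or 2.5% too small
- k = 4: sqrt(56/60) = 0.966, or 3.4% too small

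**Step 4. Actual size.** Size = 2 × P(T on N - k df > c × sqrt((N - k)/N)), where c is the critical value used: 2.001 for t on 59 df, 1.960 for the normal.

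| k | t, 59 df | Normal | Likelihood ratio |
|---|---|---|---|
| 2 | 5.39% | 5.89% | 5.50% |
| 3 | 5.61% | 6.11% | 5.72% |
| 4 | 5.83% | 6.35% | 5.94% |

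At 25% attrition, 75 × 0.75 is about 56 completers, and the t column becomes 5.4-5.9%.

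**Step 5. If one residual variance is used for both arms.** The table shows the simulated size of the maximum-likelihood test (k = 2, t on 59 df). The SD ratios and completer splits are illustrative, because the plan gives neither.

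| Completers, exercise/control | SD ratio 0.8 | 1 | 1.25 | 1.5 | 2 |
|---|---|---|---|---|---|
| 30/30 | 5.4% | 5.4% | 5.4% | 5.5% | 5.6% |
| 26/34 | 4.7% | 5.4% | 6.1% | 6.7% | 7.7% |
| 24/36 | 4.5% | 5.4% | 6.5% | 7.5% | 8.9% |

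The ratio is the exercise-arm SD of change over the control-arm SD. The column headed 1 shows that unequal completers alone change nothing. With the split reversed (34/26), ratios of 1.25 to 2 give 4.7% down to 3.8%. Entries carry simulation error of about 0.1 point.

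**Step 6. After the fix.** Arm-specific variances with Satterthwaite degrees of freedom give about 5% (4.9-5.1%) in these settings.

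**The case against.** The strongest reply is that the proven effect is tiny. An excess of 0.4 to 0.8 percentage points (t reference) would alter only a result that lands very close to p = .05. That stands, and it sets the weight of this point.

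A reader might infer that the plan assumes one error variance for both arms. It does not say so. A single undifferentiated error term makes that a natural way to code the model, but the structure is simply unspecified.

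A reader might also infer that the error rate climbs if the exercise arm loses more people. The documents do not support this. Loss alone leaves the rate at about 5.4%. A rise also needs a pooled variance and a larger spread of change in the exercise arm, and with a smaller spread there the rate falls below 5%. The plan expects equal arms. The contact schedule under Accountability Procedures for the Study Intervention ("The research staff will have regular contact (approximately 5 days/week) with subjects in the Aerobic Exercise group", against roughly twice monthly for controls) is offered there as an aid to adherence, so it is no evidence of greater exercise-arm loss.

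Larger inflation could be calculated for purely between-person contrasts in the same model, but the decision rule does not use them.

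Finally, moving to a linear model replaces the planned nonlinear function and is more than a change of options. That is correct and should be said openly. Nothing is lost for the primary comparison, because two visits cannot identify a nonlinear time curve.

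**Conclusion.** The point holds, and it is minor. As written, the decision test does not deliver its stated 5%: its size is about 5.4-5.8% with a t reference on 59 degrees of freedom, 5.5-5.9% by likelihood ratio, and 5.9-6.3% with a normal reference. Each of these references exceeds 5%, and the plan chooses none of them.

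The figures rest on 60 completers, two visits, a linear mean, arms that are equally variable or equal in size, and at most two time-varying covariates. A longer covariate list would raise them. Blood is also drawn at weeks 4 and 8 (Follow-up Testing). If sRAGE from those draws entered the primary model, the two-visit figures would not apply.

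The variance-by-arm results are conditional illustrations. They justify stating the variance structure in advance. They do not show that the trial's error rate will be 6% to 9%.

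**What to change.** In Statistics and Sample Size Considerations, state that the decision test and its confidence interval come from a linear mixed model fitted by REML (for example PROC MIXED), with:

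- time as a two-level factor, and the group-by-time term as the tested effect;
- residual variance estimated separately by arm;
- Kenward-Roger or Satterthwaite degrees of freedom.

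Say explicitly that this replaces the nonlinear function for the primary comparison, and that PROC NLMIXED Wald tests are not used for the p<.05 rule.

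**Cost:** a few sentences of analysis text and one extra variance parameter. From the standard-error ratios above, the interval widens by about 1.7% without time-varying covariates (1/0.983 = 1.017) and 3.5% with both (1/0.966 = 1.035). No change to data collection or sample size is needed.

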Figure 2 provides a general framework of the study design. This 12-week clinical study involves the testing and training of middle age to older (40 - 75 y), overweight or obese adults (BMI 26 - 44 kg/m²) with type 2 diabetes (T2DM). Sixty subjects will be randomized to 12 weeks of aerobic exercise training plus standard care (Aerobic Exercise group; n=30) or standard care only (Control group; n=30). Subjects randomized to the Control group will be given the option of an off-label exercise intervention. Therefore, Control group participants will be allowed to enroll in the AE training group after completion of the original Control group trial period. All subjects will undergo the same baseline and post testing for basal metabolic rate, maximal aerobic capacity (VO₂max), body composition, insulin sensitivity, and microdialysis sampling coupled with muscle biopsies during an acute aerobic exercise trial before.

Due to the complexity of this study, an interdisciplinary research team with experience in clinical trials, pathophysiology of, and research in obesity, insulin resistance and T2DM, vascular function, aerobic exercise testing/training, clinical medicine, biotechnology, and advanced biostatistics has been assembled. The research staff has many years (>10 y) of direct research experience with human subjects and have been trained by experts in the field and University of Michigan protocols and guidelines.

Primary Outcome Measure

1) Quantify the change in basal circulating sRAGE after 12-weeks of supervised aerobic exercise training.

Serum will be separated from blood samples collected in vacutainer tubes via centrifugation before and after 12-weeks of aerobic exercise training. sRAGE will be quantified in these serum samples via ELISA (Quantikine, Human RAGE Immunoassay) per manufacture's protocol.

Secondary Outcome Measures

1) Quantify the change in basal muscle RAGE expression after 12-weeks of supervised aerobic exercise training.

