All subjects will return for follow-up testing at approximately weeks 4 and 8. Each subject will have a blood draw (~20 ml) and the AE group will also complete a VO₂max test to adjust target HR for the training protocol.

Final Study Visit Testing

The final study visit at MCRU or Domino Farms will include the same testing procedures for both groups that were completed during baseline testing (i.e., body

composition assessment, cognitive assessment, OGTT, measurement of insulin sensitivity). In addition, all subjects will undergo an acute aerobic exercise bout (treadmill walking) coupled with microdialysis and muscle biopsies.

Total Study Tissue Sampling

Table 1 outlines the approximate amount tissue to be collected during the study. Tissue samples (blood, urine, and muscle) will be obtained during the screening and/or baseline (before the 3 month AE intervention or control period), follow-up visits, and final study visits (after the 3 month AE intervention or control period) time points. Therefore, these time points will be separated by >3 months. In addition, participants in this study will be overweight or obese and have a body weight > 110 lb. Thus, the proposed blood draws are acceptable by University of Michigan IRBMED guidelines.

Table 1		
Time point	Blood	Muscle
Screening Visit		
Both groups	20 ml	-
Baseline Visit		
AE group	280 ml	400 mg
Control group	280 ml	400 mg
Initial Exercise Bout		
AE group	80 ml	-
Control group	80 ml	-
Follow-up Visits		
Both groups	40 ml	-
Final Visit		
AE group	280 ml	400 mg
Control group	280 ml	400 mg
AE group total	~700 ml	~800 mg
Control group total	~700 ml	~800 mg

Sample Preparation, Storage, and Shipping

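### The post-hoc estimate of the training effect is not anchored on the baseline outcome, so it can disagree with the group-by-time test when pre-post correlation is high

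*Combined protocol and SAP*

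**What the plan says.** Under STATISTICAL CONSIDERATIONS, Statistics and Sample Size Considerations, the decision rule is "we will reject null hypothesis if significant (p<.05) interaction effect between group and time is observed". The next sentence adds the descriptive step: "Post-hoc analysis will examine differences between groups at different time points to assess the effect of exercise training on the outcome variables". It ends by placing that assessment over the course of the intervention.

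The same paragraph describes the model. Comparisons are made with "appropriate adjustments for fixed (age, sex, medications, diabetes duration and severity) and time-varying covariates", the examples of the latter being weight and BMI, and "we will treat training group as main fixed effect, intercept as random effects". The outcome's own baseline value is not listed.

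The primary outcome is defined as a change, under Primary Outcome Measure: "Quantify the change in basal circulating sRAGE after 12-weeks of supervised aerobic exercise training". The statistics section places the primary outcomes at two times, "collecting data at pre-aerobic exercise training and 12 weeks of training". Follow-up Testing adds visits with a blood draw in both groups: "All subjects will return for follow-up testing at approximately weeks 4 and 8". The documents do not say whether sRAGE is measured in those samples. Group Assignment Procedure describes balance between groups on sex only.

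**The concern.** With two visits and a linear parameterisation, the group-by-time interaction is the between-group difference in change. That matches the primary outcome and the sample-size wording, which also speaks of a pre-post difference between groups. The post-hoc step is the one meant to describe the training effect, and it uses another contrast: the gap between groups at a visit. For a single trial,

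week-12 difference = baseline gap + difference in change.

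If the groups differ by chance at baseline and people largely keep their rank over 12 weeks, much of that gap is still present at week 12. The report could then show a significant interaction next to no significant difference at week 12, or an effect estimate that is partly a pre-existing gap. The random intercept does not cure this. It models within-person correlation, but with a free group term the two baseline means may still differ. Nothing in the plan says which of the two figures is the effect estimate.

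**Working it through.** **Inputs.** From the statistics section: 30 per arm after attrition, two-sided alpha 0.05, 90% power, a difference of 1.24 standard units. Not in the documents: the pre-post correlation r, and which SD the standard unit refers to. I assume equal variances at both visits, normal data and no covariates, and vary r.

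**The plan's own figure.** If 1.24 is in cross-sectional SD units and the comparison has unit SD, n per arm = 2 × (1.960 + 1.282)² / 1.24² = 13.7, so 14 per arm (28 in total), not 30. With 30 per arm, power is 99.8%. The stated 60 does not reproduce on this plain reading, so both readings of the unit are carried below. The attrition step does reproduce at 20%: 60 / (1 − 0.20) = 75.

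**Chance baseline gap.** SD = √(2/30) = 0.258 outcome SD, with a 95% range of ±0.51. The regression of the week-12 difference on the baseline gap has slope r (confirmed by simulation), so the expected carry-over is r × gap. Averaged over randomisations, the week-12 difference equals the true effect.

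**Standard errors, 30 per arm, in outcome SD units.**
- Week-12 difference without baseline: √(2/30) = 0.258
- Difference in change: 0.258 × √(2(1 − r))
- Baseline-adjusted difference: 0.258 × √(1 − r²)

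| r | week 12 only | change | baseline-adjusted |
|---|---|---|---|
| 0.25 | 0.258 | 0.316 | 0.250 |
| 0.5 | 0.258 | 0.258 | 0.224 |
| 0.7 | 0.258 | 0.200 | 0.184 |
| 0.9 | 0.258 | 0.115 | 0.113 |

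**Disagreement at an effect giving the interaction 90% power.** Effect d = 3.242 × SE(change). Week-12 power = Φ(d / 0.258 − 1.96). For r = 0.7: d = 3.242 × 0.200 = 0.648, and Φ(2.51 − 1.96) = 71%. The last column comes from simulated trials (bivariate normal data, two-sided t tests).

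| r | d (SD) | week-12 power | week 12 non-significant, given a significant interaction |
|---|---|---|---|
| 0.25 | 1.02 | 98% | 1% |
| 0.5 | 0.84 | 90% | 8% |
| 0.7 | 0.65 | 71% | 26% |
| 0.9 | 0.37 | 30% | 68% |

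**Disagreement at the planned 1.24 units.**
- Unit = cross-sectional SD: about 0.3% or less of significant interactions, for r from 0.25 to 0.9.
- Unit = SD of change: the effect in outcome SD is 1.24 × √(2(1 − r)) = 0.96, 0.78 and 0.55 at r = 0.7, 0.8 and 0.9. Week-12 power is 95%, 85% and 56%, and disagreement is about 5%, 15% and 44%.

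**The case against.** The best defence is that the interaction alone decides the trial. Nothing lets the post-hoc step overturn it, and with two visits the planned model already yields the difference in change. That stands, and it limits the point to estimation and reporting.

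Several stronger readings are tempting, and the documents do not support them:

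- *The plan tests the baseline difference as a training effect.* The post-hoc sentence refers to time points during the intervention, and no between-group test at baseline is stated. Weeks 4 and 8 may be among the points meant.
- *The comparison is of raw means.* The section describes a covariate-adjusted mixed model. The listed covariates could remove part of the gap and lower the residual correlation, so the figures above, which are unadjusted, lean towards the high side. The outcome's baseline value is still absent from the list.
- *The whole baseline gap is carried as bias.* The sum of baseline gap and change is exact in any one trial, but the expected carry-over is r times the gap, and there is no bias over randomisations.
- *The week-12 contrast is always the noisier one.* Below r = 0.5 it is more precise than the difference in change (0.258 against 0.316 at r = 0.25). This is why the remedy should be baseline adjustment and not a switch to change scores alone.

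It is also fair to say that disagreement is rare if the true effect is as large as 1.24 cross-sectional SD. That protection depends on a unit that the plan does not define. The 1.24 is also given for RAGE, with no separate figure for the primary sRAGE outcome.

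**Conclusion.** The point holds in a limited form. The contrast named for describing the training effect is not anchored on baseline, while the decision test and the primary outcome both concern change. The two can disagree in a single trial, mainly when r is high and the effect is moderate. At 90% interaction power the disagreement runs from 1% (r = 0.25) to 68% (r = 0.9). At 1.24 units it is about 0.3% or up to about 44%, depending on what the unit means. These figures assume 30 per arm, equal variances, normal data and no covariate adjustment.

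A reader might infer that the trial's conclusion is at risk. It is not: rejection of the null rests on the interaction throughout. What is at risk is a coherent and precise effect estimate. Baseline adjustment has the smallest standard error at every r examined. At r = 0.7 it is 0.184 against 0.258, a reduction of 1 − 0.184/0.258 = 29%.

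**What to change.** Replace the post-hoc sentence with:

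> The effect of training at each analysed post-baseline visit is the baseline-adjusted between-group difference (baseline outcome as covariate, or a common baseline mean for both arms in the mixed model), reported with its 95% confidence interval alongside the difference in change that corresponds to the interaction test. Any between-group difference at baseline is descriptive and is not evidence of a training effect.

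Choose one of the two forms of adjustment before outcome data are examined. If baseline enters as a covariate, it should not also be a response in that same model. State whether weeks 4 and 8 are analysed visits for sRAGE. The interaction test stays as it is.

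The cost is one sentence of analysis text. The baseline values are already collected, so no participants, visits or assays are added.
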